## 5.10 EVALUATIONS AT END OF TREATMENT

The *end-of-treatment visit* (EOT) should take place approximately 30 days ( $\pm$  one week) of the last plitidepsin administration or as soon as possible after the End of Cycle 6 radiological and clinical assessments (if the patient discontinues), unless the patient

---

 When PET-CT is performed it must be in combination with diagnostic quality CT with intravenous contrast (except medically contraindicated). Two alternatives are allowed: Hybrid PET CT scanners may be used to acquire diagnostic quality CT which includes intravenous contrast OR PET CT without intravenous contrast and diagnostic quality CT images with intravenous contrast using a standalone CT scanner must be performed.

starts any subsequent antitumor therapy, in which case the EOT visit should be performed immediately before the start of the new therapy (ideally the day before or the same day): see also [Figure 3. Study design](#).

Treated patients, regardless of the reason for ending the treatment, will undergo the following EOT assessments:

- Assessment of disease-related symptoms.
- Complete physical examination (including weight and BSA).
- Basic neurological examination.
- ECOG PS.
- Vital signs (heart rate, blood pressure, body temperature).
- Concomitant therapies.
- Hematology.
- Biochemistry-A.
- Biochemistry-B.
- Pregnancy test.
- Coagulation tests.
- Serum immunoglobulin quantification.
- Serum protein electrophoresis.
- Adverse events.

For individual patients (and if clinically indicated according to Investigator's criteria), it might also include the following:

- Chest X-ray (if needed).
- Bone marrow biopsy/aspirate (if involved at diagnosis).
- Other tests as appropriate.

All these evaluations will only have to be repeated for those parameters for which no measurement is available within ten days before the EOT visit, or for those parameters with values that were out of range in the last assessment (grade  $\geq 2$  according to NCI-CTCAE v.4).

Adverse events must be reported during 30 days after the last study drug administration. All serious adverse events (SAEs) occurring within 30 days of the last study drug administration will be reported. Beyond this period of time, only those suspected to be treatment-related SAEs will be reported (Section [8.6.2](#)).

The Sponsor will evaluate all safety information that is spontaneously reported by an Investigator beyond the time frame specified in the protocol.

Failure to attend the EOT visit exclusively due to a deteriorated clinical condition will not be considered a protocol deviation.

## **5.11 FOLLOW-UP AFTER END-OF-TREATMENT VISIT**

The date and reason of the study discontinuation will be recorded on the patient's e-CRF (see Section [5.2.1.1](#)).

Patients who discontinue treatment without disease progression will be followed every four months (+ two weeks) for the first two years of follow-up, and every six months (+

two weeks) thereafter, unless clinically indicated, until PD, start of other antitumor therapy, death or the date of study termination (clinical cutoff), whichever occurs first. Tumor assessment (clinical and radiological using CT-scan) is required only for patients who showed clinical benefit, every four months (+ two weeks) for the first two years, and approximately every six months (+ two weeks) thereafter (unless clinically indicated).

After documented progression or start of a new antitumor therapy, patients will be followed for survival approximately every four months during the first two years, and then approximately every six months until death or the date of study termination, whichever occurs first. For the purpose of collecting information on the patient's survival exclusively, a documented telephone call would be acceptable; follow-up for survival will be completed for all patients only if results of the primary endpoint confirm the trial as positive.

The end-of-study date (clinical cutoff) is defined as 12 months after the last patient's inclusion. If there are patients still being treated at the planned cutoff date, the actual cutoff date will be the date when those patients have completed the ongoing treatment cycle and the corresponding EOT visit. The study will be closed earlier than planned if fewer than 15 patients are recruited in the first year after most sites are in active enrollment.

All AEs suspected to be related to the study treatment must be followed every four weeks after the end of treatment until the event or its sequelae resolve or stabilize at a level acceptable to the Investigator and the clinical monitor or his/her designated representative.

Patients who withdraw consent will not be followed with any study procedures (unless only consent to treatment was withdrawn).

Additional parameters and/or increased frequency of observations should be performed at the Investigator's discretion and according to the nature of the observed AEs. When available, autopsy data should be provided in case of death possibly related to treatment.

## **5.12 INDEPENDENT REVIEW COMMITTEE**

Radiological tumor assessment and all efficacy data will be reviewed and evaluated by an Independent Review Committee (IRC) made up of radiologists and hematologists. Operational details and instructions to centers on the data entry and transfer will be given in a separate charter.

## **5.13 INDEPENDENT DATA MONITORING COMMITTEE**

An independent expert advisory group commissioned by the Sponsor will evaluate efficacy and safety data in enrolled patients. The primary objectives of this Independent Data Monitoring Committee (IDMC) are as follows:

- To maintain the integrity of the trial conduct, to evaluate risk/benefit where possible of the APL-B-021-13 patients by monitoring the efficacy and safety data and making recommendations regarding treatment continuation and options for those on active treatment.
- To inform the Sponsor's Executive Committee regarding the outcome of the planned futility analyses as specified in the trial's Statistical Analysis Plan (SAP) and to make recommendations.

The IDMC's procedures will be detailed in a separate charter: investigators may be expected to provide complete and timely patient data for committee meetings in addition to normal CRF data entry.

## 6. PHARMACOKINETICS

All patients included in the study will be sampled for PK.

All sample collection dates and times will be recorded on the CRF. Samples will be obtained on infusion days, i.e., Days 1, 8 and 15 of the Cycle 1 for the PK analysis of plitidepsin.

Twelve blood samples will be collected at the time points detailed in [Table 6](#) for the determination of whole blood concentrations of plitidepsin.

[figure not shown]
**Table 6.** Sampling schedule for the determination of plitidepsin, including concomitant ECG measurements.

Sample Number	Day	Absolute time (h) from the start of plitidepsin infusion	Time-points for plitidepsin samples	ECG measurement
1 #	1	0	Just before first infusion	Just before first infusion
2	1	1	Just before EOI	At EOI
3	1	1.5	30 min after EOI	30 min after EOI
4	1	2	1h after EOI	1h after EOI
5	1	4	3h after EOI	-
6	1	6	5h after EOI	-
7	8	168	Just before Day 8 infusion start	Just before Day 8 infusion start
8	8	1	Just before EOI	-
9	8	2	1h after EOI	1h after EOI
10	15	168	Just before Day 15 infusion start	Just before Day 15 infusion start
11	15	1	Just before EOI	-
12	15	2	1h after EOI	1h after EOI

EOI, End of infusion; h, hour.

# Apart from the first PK sample (2 mL), a second sample (10 mL in total: 6 mL whole blood sample and 4 mL to obtain plasma) for biomarker analysis review should be drawn at this time-point.

**Figure 4.** PK sampling schedule during Cycle 1

The sampling times may be changed while maintaining or decreasing the total number and volume of samples if information obtained during the evaluation allows improvement of the schedule. Samples for the measurement of plitidepsin will have a volume of 2 mL.

The accurate recording of actual dosing and sampling times is much more important than the strict adherence to the scheduled times. The exact recording of the time of drug administration and sampling times is crucial on treatment days with PK sampling (and should be noted accurately even if not according to the planned time schedule). The infusion rate of plitidepsin will be established in order to ensure that the total dose is infused in 1 h. The drug will be infused at a constant rate throughout the 1-hour period. In order to obtain reliable PK information, the infusion rate should not be modified once the infusion begins. If a variation in the infusion time does occur, it is very important to reflect this in the e-CRF, writing clearly the time of the beginning and the end of the infusion. The infusion rate should not be changed to maintain the scheduled duration of infusion. It would be enough just to record the actual duration in the CRF and on the PK sampling sheet.

Blood samples for PK will be obtained through a peripheral vein located in the contralateral side to that of administration of plitidepsin. In any case, the sampling vein has to be different to that in which drugs are administered. Even the last sample must never be collected from the catheter used for the drug administration.

If the blood sample is obtained from a catheter, the first milliliter (mL) of blood will be discarded to avoid the dilution of the sample with the solution used to keep it clean. Heparin (10 U/mL in normal saline solution) or a slow drip of normal saline solution (10 mL/h) can be used to keep the catheter permeable between extractions.

Samples should be collected in a sodium heparin tube and gently inverted several times to ensure proper mixing. After sampling, the test tubes containing the blood samples will be immediately frozen until analysis.

All material for PK procedures will be provided by the Sponsor. A separate instruction manual for sites describing sample extraction, labeling, storage, and shipment will be provided as a separate document.

## **7. TREATMENT**

### **7.1 DESCRIPTION OF TREATMENT**

#### **7.1.1 Drug Formulation and Supply**

Plitidepsin will be supplied as a powder and solvent for concentrate for solution for infusion. The 2-mg vial should be reconstituted with a 4-mL ampoule of reconstitution solution. The list of excipients is: D-mannitol, nitrogen, polyoxyl 35 castor oil (Macrogolglycerol Ricinoleate Ph.Eur.), absolute ethanol, and water for injections. The composition of the reconstitution solution is: polyoxyl 35 castor oil/ethanol/water for injection (15/15/70% v/v/v).

For instructions regarding drug inventory, handling, reconstitution, dilution, storage, accountability and disposal, please refer to the Preparation Guide for plitidepsin and the Aplidin® IB, both provided as separate documents.

## 7.2 ADMINISTRATION OF STUDY MEDICATION

Plitidepsin will be administered intravenously as a 1-hour infusion (fixed rate) via central or peripheral venous catheter.

Patients will receive plitidepsin at a starting dose of 3.2 mg/m^2 on Day 1, 8 and 15 every four weeks (q4wk). A 1-day window is allowed for plitidepsin administration.

A cycle is defined as a four-week period.

## 7.3 PROPHYLACTIC MEDICATION

All patients must receive the following prophylactic medication 30–60 min before infusion of plitidepsin:

- 1) Dexamethasone (8 mg i.v. or equivalent)
- 2) 5-HT3 receptor antagonist: palonosetron 0.25 mg i.v. or tropisetron 5 mg i.v. or granisetron 3 mg i.v. (avoid ondansetron as this drug is categorized within a known risk of producing Torsade de Pointes) (see [Appendix 8](#)). Alternatively, metoclopramide or other antiemetic drugs may be used instead as per Investigator's criteria/institutional guidelines, and
- 3) Diphenhydramine hydrochloride 25 mg i.v. or equivalent, and
- 4) Ranitidine 50 mg i.v. or equivalent.

Oral metoclopramide and/or extended oral 5-HT3 receptor antagonist may be used as per Investigator's criteria/institutional guidelines. Additional dexamethasone can only be used as an antiemetic in the event alternative antiemetics cannot be used; and only if the Investigator considers the options above as insufficient.

## 7.4 CRITERIA FOR TREATMENT CONTINUATION

Patients can receive plitidepsin infusions (Day 1, 8, 15 of each cycle) for a maximum of six cycles (unless with PR or SD after Cycle 6: see Section [5.2.1.2](#)) if they fulfill the following requirements:

- ANC  $\geq 1.0 \times 10^9/L$ .
- Platelet count  $\geq 75 \times 10^9/L$ .
- Hemoglobin  $\geq 9.0$  g/dL.
- Calculated CrCL  $\geq 30$  mL/min (Cockcroft-Gault formula).
- Total bilirubin  $\leq 1.5 \times$  ULN ( $\leq$  grade 1).
- AST, ALT  $\leq 3.0 \times$  ULN ( $\leq$  grade 1).
- Normal value of electrolytes, including potassium, magnesium and calcium.
- Muscular toxicity (myalgia, muscular weakness, CPK increase)  $<$  grade 2.
- Other non-hematological drug-related AEs [except for increased gamma glutamyltransferase (GGT), not optimally treated nausea and vomiting, hypertension or alopecia]  $\leq$  grade 1.
- No clinically relevant ECG changes compared with grade at baseline.
- QTc must be  $\leq$  grade 1 before receiving the study treatment. In case of grade 1 QTc prolongation during treatment, and after discussion with the Sponsor, treatment must be continued with a normal value of electrolytes, including potassium, magnesium and calcium, being mandatory before the re-administration of plitidepsin.

- In case of QTc  $\geq$  grade 2, the study treatment must be discontinued, and the patient must be followed until recovery.

If these criteria are not met on Day 1 of any cycle after Cycle 1, the new cycle is to be delayed for up to two weeks until recovery. If these toxicities do not recover after a 2-week delay, the patient is to discontinue treatment and start the follow-up period unless there is obvious clinical benefit, in which case the patient might restart treatment at the Investigator’s discretion and after obtaining the approval of the Sponsor.

If these criteria are not met on Day 8 and 15 of any cycle (including Cycle 1), the scheduled infusion is to be omitted. Omitted doses for a given cycle are not to be recovered.

“Cycle delay”, therefore, is only applicable to the first infusion of a new cycle (i.e., Day 1) and not when an infusion takes place within the protocol-permitted window (one day) and not when treatment resumes after radiological assessment (see Section 5.10).

## 7.5 DOSE REDUCTION

Dose adjustments are to be based on the worst toxicity occurring during the previous cycle. [Table 7](#) shows the plitidepsin dose levels used in this study.

**Table 7. Dose levels.**

Dose level	Plitidepsin dose (mg/m  )
0	3.2
-1	2.7
-2	2.3

Once the dose given to a patient is reduced, it cannot be re-escalated. Patients requiring dose reduction below dose level -2 are to discontinue treatment and start the follow-up period (except in cases of obvious clinical benefit when further dosing changes must be agreed with the Sponsor).

The plitidepsin dose should be reduced if the patient meets any of the following criteria:

- Less than 50% compliance with the treatment schedule.
- Febrile neutropenia.
- Grade 4 neutropenia and infection, or grade 4 neutropenia lasting > 7 days.
- Grade 4 thrombocytopenia.
- Grade  $\geq$  2 muscular toxicity (weakness, myalgia and/or CPK elevations).
- Grade  $\geq$  3 AST/ALT increase.
- Any grade  $\geq$  3 clinically relevant, non-hematological toxicity (except non-optimally treated nausea and vomiting, diarrhea lasting < 48 h and/or grade  $\geq$  3 fatigue lasting < 5 days).

## 7.6 CONCOMITANT MEDICATION

All treatments received by the patient during the on-treatment period of the trial must be documented in the e-CRF. The details to be entered for each type of treatment will depend on factors such as relationship to, for example, AEs, underlying disease and symptoms, and will be defined in the study’s Monitoring Plan.

### 7.6.1 Allowed Medications/Therapies

- 1) Erythropoietin.

- 2) Therapies for the treatment of pre-existing and/or emergent medical conditions not specifically forbidden as per protocol elsewhere.
- 3) Anti-emetics according to institutional or ASCO guidelines.
- 4) G-CSFs according to institutional or ASCO guidelines (except for primary prophylaxis and when screening for eligibility).
- 5) Systemic and/or local therapies for symptomatic relief, particularly in the case of diarrhea or skin toxicity.
- 6) Adequate analgesic medication, including opioids for symptomatic pain relief if indicated.

#### **7.6.1.1 Transfusions**

Platelet and red cells transfusions are allowed within one week prior to the infusion and during the study.

#### **7.6.2 Prohibited Medications/Therapies**

- 1) Concomitant administration of any other antineoplastic therapy.
- 2) Other investigational agents.
- 3) Immunosuppressive therapies, except hydrocortisone used on isolated occasions as treatment for hypersensitivity reactions, or for the relief of the symptoms derived from the disease, if required.
- 4) Primary prophylaxis with colony-stimulating factors such as G-CSF.
- 5) Any medication with known risk of producing Torsade de Pointes, including ondansetron (see [Appendix 8](#)).

### **7.7 DRUG ACCOUNTABILITY**

Proper drug accountability will be done by the pharmacist and/or appropriately trained study personnel. Each study site will keep records to allow a comparison of quantities of drug received and used at each site for monitoring purposes. The Investigator at each study site will be the person ultimately responsible for drug accountability at the site.

All unused drug supplied by the Sponsor will be properly destroyed at the study site. Documentation of this procedure must be provided to the clinical trial monitor. If the Sponsor agrees, unused drug supplies may be returned to the drug repository.

### **7.8 TREATMENT COMPLIANCE**

The Investigator is ultimately responsible for supervising compliance with the instructions described in this study protocol.

## **8. STUDY EVALUATIONS**

### **8.1 EFFICACY**

The aim of this clinical trial is to determine the antitumor activity of plitidepsin in patients with AITL. The primary endpoint will be the ORR according to the Lugano classification response criteria per independent central review (see Section [3.1](#) and [Appendix 2](#) for more details). Secondary endpoints of efficacy include ORR per investigator assessment (IA), CR, DoR, PFS, PFS6/12, OS and OS6/12 (see Section [3.2](#) for more details).

All eligible and treated patients with AITL diagnosis confirmed after central pathological review will be included in the main efficacy analyses (primary and secondary endpoints). If a patient is treated but AITL diagnosis is not finally confirmed after central pathological review of the biopsy (even if inclusion was approved on the basis of the local histopathological report) then an additional patient will be included. Specifically, cases with features of follicular-PTCL and PTCL-NOS with TFH phenotype or with features of progression/transformation from AITL to Diffuse Large B-cell Lymphoma need to be excluded from the main efficacy analysis so additions are permitted in the event such patients are included before (or in spite of) central pathological exclusion.

Supportive efficacy analyses will be assessed in all treated patients and in all evaluable patients—defined as eligible patients who receive at least two plitidepsin cycles in which at least two complete infusions have been administered and had at least one disease assessment—as well as in patients who discontinue treatment without Cycle 3 tumor assessment after at least two plitidepsin infusions due to disease progression (PD) (or death due to PD) or toxicity (or death due to toxicity) defined as “early PD” and “treatment failures” respectively.

Patients without confirmation of AITL by central pathological review be excluded from the main efficacy analyses but, as supportive analyses, efficacy assessment will be done including all treated patients.

Radiological tumor assessment will be performed by PET-CT in combination with diagnostic quality CT one to two weeks after last dose of Cycle 3 and at least four weeks after last dose of Cycle 6 (but no more than eight weeks), and by CT-scan every four months (+ two weeks) for the first two years, and every six months (+ two weeks) thereafter or at suspected clinical progression, unless otherwise clinically indicated. An IRC consisting of medical specialists (radiologists and hematologists) who are directly involved in the care of patients with AITL—but not investigators in this trial—will review all efficacy data (including radiological assessments, bone marrow biopsies) and will assign the best response and the date of objective response or progression/censoring according to their independent evaluation.

Two futility analyses of the primary endpoint (ORR according to the Lugano classification criteria and per IRC) are planned for the time six months after ~25% and ~50% of eligible patients have been treated (i.e., 15 and 30 patients, respectively). For example, if there are two or less responders out of 15 patients or seven or less responders out of 30 patients, according to boundaries and sample size assumptions, the alternative hypothesis could be rejected, and thus recruitment might be stopped at the time of the first or second futility analysis, respectively. Otherwise, accrual will continue to a total of 60 patients with AITL confirmed by central pathological review. This decision will be taken at the time by an IDMC. The IDMC, which will include specialists in PTCL supported by a medical statistician, will review data provided by the

---

 When PET-CT is performed it must be in combination with diagnostic quality CT with intravenous contrast (except medically contraindicated). Two alternatives are allowed: Hybrid PET CT scanners may be used to acquire diagnostic quality CT which includes intravenous contrast OR PET CT without intravenous contrast and diagnostic quality CT images with intravenous contrast using a standalone CT scanner must be performed.

Investigators, the IRC efficacy assessments and safety information and will provide advice on whether the study should continue.

Operational details (including procedures for review data submission) for the IRC and IDMC will be detailed in the corresponding charters.

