Two futility analyses of the primary endpoint (ORR according to Lugano classification response criteria and per IRC) are planned around six months after approximately 25% and 50% of eligible patients (i.e., 15 and 30 patients respectively with AITL confirmed by central pathological review) have been treated. Two or less responders out of 15 patients or seven or less responders out of 30 patients, according to boundaries and sample size assumptions, will mean that the alternative hypothesis could be rejected, and thus recruitment might be stopped at the time of the first or second futility analysis, respectively. Otherwise, accrual will continue to a total of 60 patients with AITL confirmed by central pathological review. This decision will be taken at the time by an Independent Data Monitoring Committee (IDMC). The IDMC, which will include specialists in PTCL supported by a medical statistician, will review data provided by the Investigators, the IRC efficacy assessments and safety information and will advise whether the study should continue. Recruitment can continue during the review period.

If there are 19 or more responders over the total of 60 patients, the efficacy of plitidepsin will be considered as clinically relevant in AITL patients.

Operational details for the IRC and IDMC will be detailed in the corresponding charters.

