## **9. STATISTICAL METHODS**

### **9.1 SAMPLE SIZE**

The primary endpoint for this study is ORR according to the Lugano classification criteria per independent review.

A total of 60 patients with AITL confirmed by central pathological review will be treated, 19 or more responders will be needed to get an overall estimate for response rate higher than 30% and its lower limit for the 95% confidence interval greater than 20% (31.7% CI95% 20.3%–45.0% following the binomial distribution).

The type I error (alpha) associated with this one-sided test is 0.025 and the type II error (beta) is 0.1; hence, statistical power is 90%. The null hypothesis (H0) is set at ORR  $\leq$  20% ( $P_0=0.208$ ) versus the alternative hypothesis (H1) at  $\geq$  40% patients ( $P_a=0.41$ ) having an objective response, the variance of the standardized test is under the null hypothesis.

Two futility analyses of the primary endpoint (ORR according to Lugano classification and per IRC) are planned to reject the alternative hypothesis six months after 25% and 50% of eligible patients have been treated (15 and 30 patients, respectively). Pocock boundary and the actual number of patients confirmed by central pathological review will be used to control type II error for both analyses. For example, if there are two or less responders out of 15 patients or seven or less responders out of 30 patients, according to boundaries and sample size assumptions, the alternative hypothesis could be rejected, and thus recruitment might be stopped at the time of the first or second futility analysis, respectively. Otherwise, accrual will continue to a total of 60 patients AITL confirmed by central pathological review. Active recruitment will not be halted while the analysis is being carried out.

Therefore, if there are 19 or more responders of 60 patients, the null hypothesis can be rejected, allowing consideration of the observed activity plitidepsin as clinically relevant in the setting of patients with AITL.

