8.9 Interim and group sequential analyses

Two futility analyses of the primary endpoint (ORR according to the Lugano classification response criteria per independent review) are planned to reject the alternative hypothesis when ~25% and ~50% of the patients have been recruited (first 15 and 30 patients, respectively). Pocock boundary and the actual number of patients confirmed by central pathological review will be used to control type II error for both analyses. For example, if there are two or less responders out of 15 patients or seven or less responders out of 30 patients, according to boundaries and sample size assumptions, the alternative hypothesis could be rejected, and thus recruitment might be stopped at the time of the first or second futility analysis, respectively.

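### The six-month futility looks fall on the opening day of the End of Cycle 6 scan window, so the latest patients can be counted on their Cycle 3 scan alone

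*Protocol*

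**What the plan says.** Protocol 8.1 places the looks "planned for the time six months after ~25% and ~50% of eligible patients have been treated", and 9.1 repeats it: "six months after 25% and 50% of eligible patients have been treated (15 and 30 patients, respectively"). Protocol 9.3 and SAP 5 carry the same six-month lag. The synopsis, protocol 3 and SAP 2 are looser; protocol 3 says the looks "are planned around six months after approximately 25% and 50% of eligible patients" have been treated. SAP 8.9 has no lag at all: the looks come "when ~25% and ~50% of the patients have been recruited (first 15 and 30 patients, respectively").

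The response scans are tied to dosing, not to the calendar. Protocol 7.2 states "A cycle is defined as a four-week period", with infusions "on Day 1, 8 and 15 every four weeks (q4wk"). The first scan is one to two weeks after the last Cycle 3 dose. The second is "at least four weeks after last dose of Cycle 6 (but no more than eight weeks"). If the Day 1 criteria for a cycle after Cycle 1 are not met, "the new cycle is to be delayed for up to two weeks until recovery" (protocol 7.4). Missed Day 8 or Day 15 infusions are omitted and not made up.

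SAP 6.1.1 counts a responder on best overall response per independent review. The example boundaries are 2 or fewer of 15 and 7 or fewer of 30, with Pa = 0.41, 90% power and success at 19 or more of 60. Neither document says how a patient whose Cycle 6 scan is outstanding counts at a look.

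**The concern.** Up to the end of Cycle 6 a patient has two scheduled chances to be scored a responder. The boundaries come from assumptions about the best response over both. If the look is made before the second scan is done and read, a patient who would first respond at Cycle 6 enters the count as a non-responder.

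This error has one direction. A missing second scan can hide a response but cannot create one, so the observed count moves only towards the boundary. At stake is a higher chance of stopping an active drug than the design assumes, and some loss of the stated power.

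**Working it through.** **1. The design figures reproduce.** The exact 95% interval for 19/60 is 20.3-45.0%, as stated. For the three-stage rule (stop at 2 or fewer of 15 or 7 or fewer of 30; succeed at 19 or more of 60), exact binomial calculation with every scan available gives:

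| True ORR | Stop at look 1 | Stop at look 2 | Total stop | Power |
|---|---|---|---|---|
| 0.41 | 2.27% | 2.50% | 4.8% | 91.7% |
| 0.40 | 2.71% | 3.14% | 5.9% | 89.5% |

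**2. Calendar, in days after first dose.** Inputs are the 28-day cycle, dosing on Days 1, 8 and 15, and the scan 28-56 days after the last Cycle 6 dose.
- Cycle 6 Day 15: 5 × 28 + 14 = 154.
- Second scan: 154 + 28 = 182 to 154 + 56 = 210.
- Day 15 omitted: 147 + 28 to 147 + 56 = 175-203. Days 8 and 15 both omitted: 140 + 28 to 140 + 56 = 168-196.
- Maximum two-week delay in each of Cycles 2-6: 5 × 42 + 14 = 224, so the scan falls on days 252-280.
- First scan: 2 × 28 + 14 + 7 to 14 = 77-84, and at most day 112 with maximum delays. It is due well before the look for every counted patient.
- Look: 365.25 / 2 = day 182.6 after the 15th or 30th patient's first dose.

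With no delay and Day 15 given, the scan window opens on the look date and closes about 27 days after it (210 − 182.6). IRC reading time is extra and is not given in the documents.

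**3. How many patients are exposed.** Planned accrual is 60 / 36 = 1.67 per month. If all scans fell on day 210, the 15th (or 30th) patient and on average 1.67 × 27.4 / 30.44 = 1.5 earlier ones would be pending. With scans spread uniformly over days 182-210 and mean total delays of 0, 2 and 4 weeks, simulation gives 1.7, 2.5 and 3.3 pending patients per look.

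**4. Direct check on the boundaries.** Let m patients be pending and let a share q of responses be first seen at Cycle 6. The count at look 1 is then Bin(15 − m, 0.41) + Bin(m, 0.41(1 − q)), and similarly for 30. For m = 1-3 and q = 10-50% (both assumed):
- P(2 or fewer of 15) rises from 2.3% to 2.4-4.4%.
- P(7 or fewer of 30), taken alone, rises from 3.4% to 3.6-5.4%.

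**5. Whole design.** Simulation of 200,000 trials per scenario, with random accrual at the planned rate, exponential total delay, pending late responders counted as non-responders, and every crossing treated as a stop. Power at a true ORR of 41%:

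| Responses first seen at Cycle 6 | No delay | Mean 2 weeks | Mean 4 weeks |
|---|---|---|---|
| 20% | 91.2% | 90.8% | 90.6% |
| 35% | 90.8% | 90.3% | 89.6% |
| 50% | 90.3% | 89.4% | 88.5% |

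With no pending scans the same simulation gives 91.8%. Total false stops run from 5.4% to 8.6% across the grid. At a true ORR of 40%, power falls to 85.8-88.9%, but there it is already 89.5% with every scan in hand.

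**The case against.** Several points on the other side stand.

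- **A reader might infer that the latest patients necessarily enter the look without a second scan.** The documents do not support that. The window opens on the look date, and omitted Cycle 6 doses move it earlier. Patients who progressed or left treatment after the Cycle 3 scan may have no second scan due.
- **A reader might infer that the design fails its 90% power.** It does not in general. At 41%, power drops below 90% only when about 35-50% of responses appear late and delays average two to four weeks. The documents give neither figure. The earlier PTCL cohort suggests late first responses may be few: 58.6% had progression and 20.7% stable disease as best response, with median TTP/PFS of 1.6 months. That cohort is small and not all AITL.
- **The rule is advisory.** Crossing means recruitment might be stopped. The data monitoring committee also sees investigator data and safety, so treating each crossing as a stop puts the false-stop figures at the upper end. Its charter and the IRC charter were not available and may cover pending patients.
- **The wording has slack.** The synopsis, protocol 3 and SAP 2 say around six months. Protocol 8.1, 9.1, 9.3 and SAP 5 do not, and an undefined tolerance does not ensure the scan is in.
- **Treated could mean treatment completed**, which would remove the problem. However, SAP 4.1 counts a patient as treated from part of one infusion.

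The SAP 8.9 trigger is the sharper textual conflict. Correcting it to six months would still leave this point in place.

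**Conclusion.** The point holds in a limited form. On the protocol's own schedule, a look at six months leaves no margin for the End of Cycle 6 scan, its read or any cycle delay. A few patients per look can therefore be counted on the Cycle 3 scan alone, with bias only towards stopping. Under the assumptions in the working, at a true ORR of 41%, false stops rise by about 0.6 to 3.8 percentage points (4.8% to 5.4-8.6%), and power falls by about 0.6 to 3.3 points (91.8% to 88.5-91.2%). The calendar arithmetic is firm. The size depends on the share of late responses and on delays, which the documents do not give. This is a worthwhile low-cost correction, not a flaw that invalidates the design.

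**What to change.** Use one trigger in the protocol synopsis, 3, 8.1, 9.1 and 9.3 and in SAP 2, 5 and 8.9. Each look is made when every one of the first 15 (30) centrally confirmed patients has an IRC-read End of Cycle 6 assessment, or has progressed, died or stopped treatment before it. This also removes the conflict with the recruitment trigger in SAP 8.9.

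A longer fixed lag is not a substitute. Thirty weeks, for example, is day 210, which allows nothing for delays or IRC reading. If a calendar date must stay, restrict the look to patients whose Cycle 6 assessment is complete or who ended earlier, and state that the boundary is recomputed for that number. This would be a new provision: protocol 9.1 adjusts only for the number confirmed by pathology review.

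The cost is wording plus a later look: about 1-2 months, or about 3 with maximum delays ((280 − 182.6) / 30.44 = 3.2). Recruitment continues meanwhile, so at 1.67 per month roughly 2-5 more patients are enrolled before the decision.
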